	Grade 3 (≤ 6 hours after FLX475 dose)	Withhold FLX475 treatment until AE Grade ≤1 (or to pretreatment severity grade) and then resume treatment at reduced dose: 100 mg → 50 mg	Permanently discontinued from FLX475 treatment (at 50 mg or lower dose level) or continue treatment either at 50 mg or at a reduced dose of 25 mg (If it is determined by the investigator, in consultation with the Sponsor or medical monitor, to be in the subject's best interest)	N/A	N/A
	Grade 4	Should be treated appropriately and permanently discontinued from FLX475 treatment (unless it is later determined by the investigator, in consultation with the Sponsor or medical monitor, to be in the subject's best interest to continue treatment)			

Note: For grading see CTCAE version 5.0. Collect all CTC grades of adverse events, decreasing and increasing grade.

BMI = body mass index, CTCAE = Common Terminology Criteria for Adverse Events.

- An interruption of study treatment for more than 21 days will require Sponsor's approval before treatment can be resumed.
- Initiate optimal medical management for nausea, vomiting, hypothyroidism and/or diarrhea prior to any study treatment interruption or dose reduction.

- c. Applicable only to Grade 2 toxicities judged by the subject or physician to be intolerable.
- d. Obese subjects with weight loss do not need their weight to return to baseline weight or within 10% of baseline weight (i.e., Grade 1 weight loss). These subjects will restart the study treatment(s) at a lower dose once their weight remains stable for at least 1 week and they reach their normal BMI (if the weight loss occurs but is still above normal BMI, they can restart study treatment at a lower dose once their weight has been stable for at least 1 week). Normal BMI should be used as the new baseline for further dose reductions.
- e. For Grade 3 toxicity, investigator will decide the probability of the event being related to 1 or both drugs and as to whether dose modification of either or both drugs is required.
- f. For asymptomatic laboratory abnormalities, such as Grade ≥ 3 elevations of amylase and lipase that are not considered clinically relevant by the investigator, continuation of treatment should be discussed with the Sponsor.
- g. Excluding laboratory abnormalities judged to be non-life-threatening, in which case manage as Grade 3.

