Abnormal laboratory values should not be listed as separate AEs if they are considered to be part of the clinical syndrome that is being reported as an AE. It is the responsibility of the investigator to review all laboratory findings in all subjects and determine if they constitute an AE. Medical and scientific judgment should be exercised in deciding whether an isolated laboratory abnormality should be classified as an AE. Any laboratory abnormality considered to constitute an AE should be reported on the Adverse Event eCRF.

Abnormal ECG (QTcF) results, if not otherwise considered part of a clinical symptom that is being reported as an AE, should be considered an AE if the average QTcF interval is ≥ 450 ms or there is an average increase of more than 60 ms from baseline (defined as average QTcF value from C1D1 pre-dose ECGs). Any ECG abnormality that the investigator considers as an AE should be reported as such.

Death should be considered an outcome and not a distinct event. The event or condition that caused or contributed to the fatal outcome should be recorded as the single medical concept on the Adverse Event eCRF. Generally, only one such event should be reported. If the cause of death is unknown and cannot be ascertained at the time of reporting, "unexplained death" should be recorded on the Adverse Event eCRF. If the cause of death later becomes available (e.g., after autopsy), "unexplained death" should be replaced by the established cause of death.

All AEs observed during the study will be reported on the eCRF. All AEs, SAEs, and other reportable safety events that occur after the consent form is signed must be reported by the investigator. Other events that occur prior to the consent form is signed should be recorded as medical history.

All AEs or events of clinical interest (ECIs) that occur after the consent form is signed through 30 days following cessation of study treatment must be reported on the eCRF by the investigator. See Section [9.2.2](#) for further discussion of SAEs and ECIs.

All AEs must be recorded and followed through 30 days following cessation of study treatment (or 30 days after final dose if the subject initiates new anticancer therapy), or until resolution, whichever comes first.

Every effort must be made by the investigator to categorize each AE according to its severity and its relationship to the study treatment.

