9.2.1.1. Assessing Severity of Adverse Events

Adverse events will be graded on a 5-point scale according to CTCAE v5.0 (Appendix [2](#)). Investigators will report CTCAE(v5.0) grades for all AEs (for both increasing and decreasing severity).

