#### 13.1 Adverse Events

All AEs including will be coded using the most recent version of the MedDRA coding dictionary, graded using NCI-CTCAE version 5.0.

Treatment emergent adverse events (TEAEs) are defined as adverse events occurring from the first dose of the study treatment through 30 days following cessation of study treatment will be considered 'treatment-emergent'. Adverse events that start before first study treatment and deteriorate under treatment will also be considered as 'treatment-emergent'.

All AE summaries will be restricted to TEAEs only and all the study drug related AE will be summarized [REDACTED]. Summary tables will include the number of participants (%) experiencing an event and the number of events. Subjects will be counted only once for each SOC and PT level (categorical descriptive analysis). For each TEAE, the most extreme grade recorded in eCRF will be attributed and used in the by-severity summaries.

The TEAE summaries will include:

- Overall summary of TEAEs
- Summary of TEAEs by SOC and PT
- Summary of TEAEs by SOC, PT and Severity
- Summary of SAEs by SOC and PT
- Summary of SAEs by SOC, PT and Severity
- Summary of ECIs by SOC and PT
- Summary of ECIs by SOC, PT and Severity
- Summary of TEAEs Related to (any study drug [REDACTED]) by SOC and PT
- Summary of TEAEs Related to (any study drug [REDACTED]) by SOC, PT and Severity
- Summary of SAEs related to (any study drug [REDACTED]) by SOC and PT
- Summary of TEAEs leading to (any study drug [REDACTED]) dose modification (reduction / interruption) by SOC and PT
- Summary of TEAEs leading to (any study drug [REDACTED]) discontinuation by SOC and PT
- Summary of TEAEs leading to death by SOC and PT

Separate by-subject data listings will be created for

- TEAEs
- SAEs
- TEAEs leading to dose modification (reduction/interruption)
- TEAEs leading to drug discontinuation
- TEAEs leading to death
- Adverse events reported prior to treatment but after informed consent

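### SAP 13.1 sets no first-dose limit on the grade attributed to a TEAE, so a by-severity table can show a grade that occurred only before any study drug

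*Protocol*

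**What the plan says.** **Collection.** The note under the FLX475 dose-modification table (Protocol 7.3.1) reads "Collect all CTC grades of adverse events, decreasing and increasing grade". Protocol 9.2.1.1 repeats it for all events: "Investigators will report CTCAE(v5.0) grades for all AEs (for both increasing and decreasing severity". Reporting starts at consent: "All AEs, SAEs, and other reportable safety events that occur after the consent form is signed must be reported by the investigator" (Protocol 9.2.1). Screening runs from Day -30 to Day -1, so the database can hold grades from before the first dose. Conditions that predate consent go to medical history.

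**Classification.** SAP 13.1 counts events arising from first dose through 30 days after cessation as TEAEs. It adds a second route: "Adverse events that start before first study treatment and deteriorate under treatment will also be considered" treatment-emergent. It does not say against which grade deterioration is judged.

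**Severity.** SAP 13.1: "For each TEAE, the most extreme grade recorded in eCRF will be attributed and used in the by-severity summaries". No start date is set for the grades that qualify. Protocol 11.4.3 says only that TEAEs are summarised by maximum severity.

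**Counting.** "Summary tables will include the number of participants (%) experiencing an event and the number of events". The next sentence of SAP 13.1 protects the participant column: "Subjects will be counted only once for each SOC and PT level (categorical descriptive analysis".

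**The concern.** Three rules interact. Pre-dose grades are collected, a pre-dose event can become a TEAE, and the TEAE then takes the worst grade on file. Read literally, the third rule reaches back across first dose, so a by-severity table can report a grade that the study treatment could not have caused.

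The SAP avoids this elsewhere. The laboratory and ECOG shift tables (SAP 13.2 and 13.7) set the worst value up to ED/EOT against baseline. The adverse-event severity tables have no such reference.

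The trial has no control arm and safety is a secondary objective, so no comparison group offsets a misattributed grade. Stages are small: one subject is 10% of a 10-subject stage. Two programmers could also read the sentence differently and obtain different Grade 3 or higher counts from the same data.

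**Working it through.** The plan gives no figure on this point, so there is none to reproduce. The check applies the SAP 13.1 rules literally to grade histories.

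1. **One history.** Take an event with Grade 3 then Grade 1 before dosing, and Grade 2 on treatment.
   - Classification: SAP 3.2 defines baseline as the last available value before first dose. On that convention the reference is Grade 1, Grade 2 exceeds it, and the event is a TEAE.
   - Severity as written: max(3, 1, 2) = 3.
   - Severity limited to grades on or after first dose: max(2) = 2.

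2. **When it can happen.** Let g1 and g2 be two successive pre-dose grades (1 to 4) and h1 and h2 two on-treatment grades (0 to 4). That gives 4 × 4 × 5 × 5 = 400 hypothetical histories, equally weighted.
   - *Reference = last pre-dose grade.* The event is a TEAE if max(h1, h2) > g2. For g2 = r, the number of (h1, h2) pairs is 25 − (r + 1)², which is 21, 16, 9 and 0 for r = 1 to 4, or 46 in all. With 4 values of g1, 4 × 46 = 184 TEAE histories.
   - A pre-dose grade becomes the tabulated maximum when g2 < max(h1, h2) < g1. There are 5 pairs with maximum 2 and 7 with maximum 3. The cases are g2 = 1, maximum 2, g1 = 3 or 4 (2 × 5 = 10); g2 = 1, maximum 3, g1 = 4 (7); and g2 = 2, maximum 3, g1 = 4 (7). The total is 24, and 24/184 = 13%.
   - Only the first 10 cross the Grade 3 boundary (10/184 = 5.4%). In the other 14 the on-treatment grade is already 3.
   - *Reference = highest pre-dose grade.* For M = max(g1, g2), the number of (g1, g2) pairs is 1, 3, 5 and 7 for M = 1 to 4. TEAE histories: 1 × 21 + 3 × 16 + 5 × 9 + 7 × 0 = 114. A TEAE now needs max(h1, h2) > M, so the pre-dose grade can never be the maximum: 0 of 114.

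   These shares describe equally weighted invented histories and show which pattern is needed. They are not expected rates. Events that start after first dose have no pre-dose grade and cannot be affected.

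3. **Separate grade records.** If the eCRF stored each grade change as its own event, an on-treatment course 1-2-3-2-1 would give 5 records for 1 event. The participant count for that preferred term would stay at 1 and the maximum grade at 3. Only the number-of-events column would change.

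**The case against.** The other side has four good arguments.

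- **The pattern is rare.** The event must start in the short window between consent and first dose, improve before Day 1, and then worsen on treatment to below its earlier peak. If deterioration were judged against the highest pre-dose grade, it could not occur. This stands as a limit on size. It does not remove the gap, because the SAP names no reference and its own baseline convention points to the last pre-dose value.
- **Multiple counting is not shown.** A reader might infer that one event will be counted several times, or that some table must be wrong however the eCRF is built. The documents do not support that. They do not show the eCRF layout, the eCRF completion guidelines are not among them, and parts of SAP 13.1 are redacted. Attributing one grade to each TEAE presupposes one event with several grades. Participants are counted once per SOC and PT. A screening event that merely improves after first dose does not meet the deterioration condition; it would be counted only if a grade-change date were treated as a new onset, which neither document instructs.
- **No decision rule depends on it.** The go/no-go criterion is the posterior probability for ORR, considered with overall safety, and no formal test is planned. This stands.
- **Closing the far end would do harm.** Since TEAEs are defined up to 30 days after cessation, one might also cut the grade off there. But SAEs are followed to resolution or stabilisation (Protocol 9.2.2). An event that began in the window at Grade 4 and proved fatal on day 45 after cessation would then be tabulated below Grade 5. No such cut-off should be added.

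**Conclusion.** The point holds in a narrow form. SAP 13.1, as written, allows a TEAE to carry a grade that occurred only before first dose. The literal reading gives Grade 3 where the on-treatment maximum is Grade 2, using the SAP's own baseline convention for the comparison.

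The likely size is 0 to 1 subject per stage. This is an assumption, because the documents give no rate of such histories. One subject is 10% of a 10-subject stage and 1/30 = 3.3% of 30 subjects in Cohort 1. Even that subject changes the Grade 3 or higher count only if the pre-dose grade was at least 3, the on-treatment grade was below 3, and the subject had no other TEAE of Grade 3 or higher.

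The effect is confined to descriptive safety tables. A rise of several percentage points in Grade 3 or higher incidence cannot be derived from the documents. Linking of grade records is a secondary clarification whose relevance depends on an eCRF design that is not shown.

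**What to change.** In SAP 13.1, replace the severity sentence and complete the deterioration rule with:

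> An AE that began before first dose is treatment-emergent only if its grade on or after first dose exceeds its last grade before first dose. The severity attributed to a TEAE is the worst grade recorded on or after first dose.

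Set no upper time limit on the grade of an event already classed as a TEAE, so that later worsening or a fatal outcome stays in the table. Apply the rule to every by-severity summary.

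As a secondary clarification, if the eCRF stores grade changes as separate records, state that they are linked to one event before TEAEs are classified and events are counted.

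Cost: SAP wording and one extra derivation in the adverse-event dataset, using grades already collected. Grade 3 or higher counts may fall slightly.

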7.3.2. Pembrolizumab

Adverse events associated with pembrolizumab exposure may represent an immunologic etiology. These immune-related AEs (irAEs) may occur shortly after the first dose or several months after the final dose of pembrolizumab. Therefore, early recognition and initiation of treatment is critical to reduce complications. Based on existing clinical study data, most irAEs are reversible and can be managed with interruptions of pembrolizumab, administration of corticosteroids, and/or other supportive care. Suspected irAEs should be adequately evaluated to confirm etiology or exclude other causes. Additional procedures or tests such as bronchoscopy, endoscopy, skin biopsy may be included as part of the evaluation. Based on the severity of irAEs, Pembrolizumab should be withheld or permanently discontinued, and corticosteroids administered. Pembrolizumab may cause severe or life-threatening infusion-reactions including severe hypersensitivity or anaphylaxis. Signs and symptoms usually develop during or shortly after drug infusion and generally resolve completely within 24 hours of completion of infusion.

Criteria for dose delay, modification, or discontinuation of pembrolizumab are described below, and are based on criteria in the Keytruda Investigator's Brochure.

Table 7.3:2 shows treatment guidelines, including premedications, for subjects who experience an infusion reaction associated with the administration of pembrolizumab.

Dose modification and toxicity management guidelines for irAEs associated with pembrolizumab are provided in Table 7.3:3 .

Pembrolizumab may be interrupted for situations other than treatment-related AEs, such as medical or surgical events and/or unforeseen circumstances not related to study intervention. However, pembrolizumab is to be restarted within 3 weeks of the originally scheduled dose or within 42 days of the previously administered dose, unless otherwise discussed with the Sponsor. The reason for interruption is to be documented in the subject's eCRF.

Table 7.3:2 Infusion Reaction Treatment Guidelines for Pembrolizumab

CTCAE(v5.0) Grade	Treatment	Premedication for Subsequent Doses of Pembrolizumab
Grade 1 Mild reaction; infusion interruption not indicated; intervention not indicated	Increase monitoring of vital signs as medically indicated until the participant is deemed medically stable in the opinion of the investigator.	None
Grade 2 Requires therapy or infusion interruption but responds promptly to symptomatic treatment (e.g., antihistamines, NSAIDs, narcotics, IV fluids); prophylactic medications indicated for ≤ 24 hrs.	
 • Stop Infusion. • Additional appropriate medical therapy may include but is not limited to: 
 • IV fluids • Antihistamines • NSAIDs • Acetaminophen • Narcotics • Increase monitoring of vital signs as medically indicated until the participant is deemed medically stable in the opinion of the investigator. • If symptoms resolve within 1 hour of stopping drug infusion, the infusion may be restarted at 50% of the original infusion rate (e.g. from 100 mL/hr. to 50 mL/hr.). Otherwise dosing will be held until symptoms resolve and the participant should be premedicated for the next scheduled dose. 
Participants who develop Grade 2 toxicity despite adequate premedication should be permanently discontinued from further study drug treatment
	Participant may be premedicated 1.5h (± 30 minutes) prior to infusion of study intervention with: Diphenhydramine 50 mg po (or equivalent dose of antihistamine). Acetaminophen 500-1000 mg po (or equivalent dose of analgesic).

CTCAE(v5.0) Grade	Treatment	Premedication for Subsequent Doses of Pembrolizumab
Grades 3 or 4 Grade 3: Prolonged (i.e., not rapidly responsive to symptomatic medication and/or brief interruption of infusion); recurrence of symptoms following initial improvement; hospitalization indicated for other clinical sequelae (e.g., renal impairment, pulmonary infiltrates) Grade 4: Life-threatening; pressor or ventilator support indicated	
• Stop Infusion.• Additional appropriate medical therapy may include but is not limited to:
• Epinephrine**• IV fluids• Antihistamines• NSAIDs• Acetaminophen• Narcotics• Oxygen• Pressors• Corticosteroids• Increase monitoring of vital signs as medically indicated until the participant is deemed medically stable in the opinion of the investigator.• Hospitalization may be indicated. 
**In cases of anaphylaxis, epinephrine should be used immediately. Participant is permanently discontinued from further study drug treatment.
	No subsequent dosing

Appropriate resuscitation equipment should be available at the bedside and a physician readily available during the period of drug administration. For further information, please refer to the Common Terminology Criteria for Adverse Events v5.0 (CTCAE) at <http://ctep.cancer.gov>

Table 7.3:3 Dose Modification and Toxicity Management Guidelines for Immune-related Adverse Events Associated with Pembrolizumab

Immune-related Adverse Event	Toxicity Grade or Conditions (CTCAE v5.0)	Action Taken with Pembrolizumab	irAE Management with Corticosteroids and Other Therapies	Monitoring and Follow-up
General instructions:				
	Grade 2	Withhold	Administer corticosteroids (initial dose of 1 to 2 mg/kg prednisone or equivalent) followed by taper Add prophylactic antibiotics for opportunistic infections	Monitor participants for signs and symptoms of pneumonitis Evaluate participants with suspected pneumonitis with radiographic imaging and initiate corticosteroid treatment
	Recurrent Grade 2, Grade 3 or 4	Permanently discontinue		
	Grade 2 or 3	Withhold	Administer corticosteroids (initial dose of 1 to 2 mg/kg prednisone or equivalent) followed by taper	Monitor participants for signs and symptoms of enterocolitis (ie, diarrhea, abdominal pain, blood or mucus in stool with or without fever) and of bowel perforation (ie, peritoneal signs and ileus)
	Recurrent Grade 3 or Grade 4	Permanently discontinue		Participants with \geq Grade 2 diarrhea suspecting colitis should consider GI

Immune-related Adverse Event	Toxicity Grade or Conditions (CTCAE v5.0)	Action Taken with Pembrolizumab	irAE Management with Corticosteroids and Other Therapies	Monitoring and Follow-up
				consultation and performing endoscopy to rule out colitis Participants with diarrhea/colitis should be advised to drink liberal quantities of clear fluids. If sufficient oral fluid intake is not feasible, fluid and electrolytes should be substituted via IV infusion
AST / ALT elevation or Increased bilirubin	Grade 2 ^a	Withhold	Administer corticosteroids (initial dose of 0.5 to 1 mg/kg prednisone or equivalent) followed by taper	Monitor with liver function tests (consider weekly or more frequently until liver enzyme value returned to baseline or is stable)
	Grade 3 ^b or 4 ^c	Permanently discontinue	Administer corticosteroids (initial dose of 1 to 2 mg/kg prednisone or equivalent) followed by taper	
Type 1 diabetes mellitus (T1DM) or Hyperglycemia	New onset T1DM or Grade 3 or 4 hyperglycemia associated with evidence of β -cell failure	Withhold ^d	Initiate insulin replacement therapy for participants with T1DM Administer anti-hyperglycemic in participants with hyperglycemia	Monitor participants for hyperglycemia or other signs and symptoms of diabetes
Hypophysitis	Grade 2	Withhold	Administer corticosteroids and initiate hormonal replacements as clinically indicated	Monitor for signs and symptoms of hypophysitis (including hypopituitarism and adrenal insufficiency)
	Grade 3 or 4	Withhold or permanently discontinue ^d		

Immune-related Adverse Event	Toxicity Grade or Conditions (CTCAE v5.0)	Action Taken with Pembrolizumab	irAE Management with Corticosteroids and Other Therapies	Monitoring and Follow-up
Hyperthyroidism	Grade 2	Continue	Treat with non-selective beta-blockers (eg, propranolol) or thionamides as appropriate	Monitor for signs and symptoms of thyroid disorders
	Grade 3 or 4	Withhold or permanently discontinue ^d		
Hypothyroidism	Grade 2, 3 or 4	Continue	Initiate thyroid replacement hormones (eg, levothyroxine or liothyronine) per standard of care	Monitor for signs and symptoms of thyroid disorders
Nephritis: grading according to increased creatinine or acute kidney injury	Grade 2	Withhold	Administer corticosteroids (prednisone 1 to 2 mg/kg or equivalent) followed by taper	Monitor changes of renal function
	Grade 3 or 4	Permanently discontinue		
Neurological Toxicities	Grade 2	Withhold	Based on severity of AE administer corticosteroids	Ensure adequate evaluation to confirm etiology and/or exclude other causes
	Grade 3 or 4	Permanently discontinue		
Myocarditis	Grade 2, 3 or 4	Permanently discontinue	Based on severity of AE administer corticosteroids	Ensure adequate evaluation to confirm etiology and/or exclude other causes

Immune-related Adverse Event	Toxicity Grade or Conditions (CTCAE v5.0)	Action Taken with Pembrolizumab	irAE Management with Corticosteroids and Other Therapies	Monitoring and Follow-up
Exfoliative Dermatologic Conditions	Suspected SJS, TEN, or DRESS	Withhold	Based on severity of AE administer corticosteroids	Ensure adequate evaluation to confirm etiology or exclude other causes
	Confirmed SJS, TEN, or DRESS	Permanently discontinue		
All other irAEs	Persistent Grade 2	Withhold	Based on severity of AE administer corticosteroids	Ensure adequate evaluation to confirm etiology or exclude other causes
	Grade 3	Withhold or discontinue based on the event ^e		
	Recurrent Grade 3 or Grade 4	Permanently discontinue		

Immune-related Adverse Event	Toxicity Grade or Conditions (CTCAE v5.0)	Action Taken with Pembrolizumab	irAE Management with Corticosteroids and Other Therapies	Monitoring and Follow-up

AE(s)= adverse event(s); ALT= alanine aminotransferase; AST=aspartate aminotransferase; CTCAE=Common Terminology Criteria for Adverse Events; DRESS=Drug Rash with Eosinophilia and Systemic Symptom; GI=gastrointestinal; IO=immuno-oncology; ir=immune related; IV=intravenous; SJS=Stevens-Johnson Syndrome; T1DM=type 1 diabetes mellitus; TEN=Toxic Epidermal Necrolysis; ULN=upper limit of normal.
 
Note: Non-irAE will be managed as appropriate, following clinical practice recommendations.
 
^a AST/ALT: >3.0 to 5.0 x ULN if baseline normal; >3.0 to 5.0 x baseline, if baseline abnormal; bilirubin:>1.5 to 3.0 x ULN if baseline normal; >1.5 to 3.0 x baseline if baseline abnormal
 
^b AST/ALT: >5.0 to 20.0 x ULN, if baseline normal; >5.0 to 20.0 x baseline, if baseline abnormal; bilirubin:>3.0 to 10.0 x ULN if baseline normal; >3.0 to 10.0 x baseline if baseline abnormal
 
^c AST/ALT: >20.0 x ULN, if baseline normal; >20.0 x baseline, if baseline abnormal; bilirubin: >10.0 x ULN if baseline normal; >10.0 x baseline if baseline abnormal
 
^d The decision to withhold or permanently discontinue pembrolizumab is at the discretion of the investigator or treating physician. *If control achieved or \leq Grade 2, pembrolizumab may be resumed.
 
^e Events that require discontinuation include but are not limited to: encephalitis and other clinically important irAEs (eg. vasculitis and sclerosing cholangitis).
				

